## 5 Stage 3 – THE PILOT TRIAL

The pilot trial will be a multicentre, open-label, two-group, individually randomised, controlled trial.

### 5.1 Outcome measures/endpoints

As this is a pilot trial, a number of outcome measures / endpoints will be included to establish which is the optimal one for a definitive trial.

| Objectives                             | Outcome Measures  | Time point(s) of evaluation of this outcome measure   |
|--|---|---|
| Asthma specific quality of life | 
PedsQL Asthma Module
 
This will be assessed using the validated paediatric asthma quality of life asthma module (short form) questionnaire and presented as a total score (sub-scores will also be presented)([24]).
 
From the adult BREATHE study [2] we expect the intervention to have most benefit on asthma related quality of life. This is also an important patient outcome.
 
As the questionnaire does not have complete coverage for emotional issues, some additional questions will also be asked [25].
 
This is the expected primary outcome for the definitive phase III study.
 | Baseline, after 2 months and at the end of the study after 6 months.  |
|  | 
Paediatric asthma quality of life
 
This will be assessed using the validated paediatric asthma quality of life questionnaire and presented as a total score (sub-scores will also be presented) [26].
 
It is not possible for this to be recorded for all participants as the copyright owner does not allow it to be used as an online questionnaire.
  | Baseline, after 2 months and at the end of the study after 6 months for participants seen in person, where they can post a paper questionnaire to the |

|                               |  |  |
|-------------------------------|--|--|
|                               |  | study team or complete it over the telephone.                        |
| Asthma control         | This will be assessed using the validated asthma control test and presented as a total score [27]. This is an important asthma endpoint reflecting the presence of ongoing symptoms, impact on quality of life and likely risk of an exacerbation.   | Baseline, after 2 months and at the end of the study after 6 months. |
| Healthcare utilisation | 
This will be assessed using a very short questionnaire. It will be presented as:
 
 
Episodes of prescriptions of 3 or more days of prednisolone (or similar),
 
attendance at emergency department for an exacerbation of asthma,
 
hospital admission for an exacerbation of asthma.
 
 
Unplanned healthcare utilisation represents a disruption to the lives of patients and families and a major cost of the NHS.
 | Baseline, after 2 months and at the end of the study after 6 months. |

## 5.2 Trial design

The pilot trial will aim to assess the acceptability, uptake and success in collecting follow up data and variance in asthma-related outcome measures. A parallel group design will be used with participants being randomised to intervention or normal management. The intervention will be a self-guided, breathing retraining digital intervention, delivered via a mobile-friendly, online platform. The intervention will continue to be used for 6 months after which both groups will be reassessed. The usual management control group will then have access to the intervention (delayed access).

## 5.3 Trial setting

The setting is primary and secondary care in England. Recruitment would be from primary care and hospital clinics. Asthma UK will sign-post potential recruits to the website. Participants will access the trial via a web-based platform.

## 5.4 Participant eligibility criteria

### Inclusion criteria

- Young people aged 12-17 years
- Physician diagnosed asthma
- Impaired quality of life (<85)
- Under the care of a general practitioner, community or hospital practitioner for their asthma

### Exclusion criteria

- Co-existent respiratory conditions such as bronchiectasis
- Already using breathing techniques
- Already enrolled in another interventional study
- Lack of informed consent
- Learning difficulties

## 5.5 Trial procedures

The trial procedures are summarised in Figure 3 below.

### 5.5.1 Recruitment and identification

[figure not shown]
Adolescent with asthma will be recruited in a number of ways:

- 20 secondary clinics in Southampton, Isle of Wight and other centres:
  - (i) database search by NHS staff with invitation letters; invitation letters will be sent; letter will invite interested adolescents;
  - (ii) opportunistically via posters in clinics and clinic staff mentioning to potential participants; poster will invite interested adolescents.
- Up to 20 local primary care clinics (general practitioner, primary care nurses and community nurses) who will be study participant identification centres (PICs):
  - (i) primary care staff will perform a database search; invitation letters will be sent; letter will invite interested adolescents;
  - (ii) opportunistically via posters in surgeries and primary care staff mentioning to potential participants; poster will invite interested adolescents.
- Asthma UK – advert in newsletters, on website and social media inviting interested adolescents.
- Social media (eg Twitter, Instagram, Facebook) adverts and flyers - those interested will click a button/link which opens the BREATHE4T study website where they can leave their details for the study team to contact them.
- Professional networks (eg respiratory and paediatric physio teams informing patients of the study)
- Snowballing
- Posters, adverts and flyers in various local locations (examples include GP surgeries, chemists, supermarket notice boards, schools, colleges, leisure and sport clubs, coffee shops, asthma support groups and charities (e.g. No Limits), local newspapers)
- Press release

This approach will mean that we will not be able to identify the total number of potential participants who would have seen information about the trial and we will not have information about their basic demographics nor asthma status.

**Figure 3. Overview of participant journey in the Stage 3 pilot study**

**Participants journey in the study**

### 5.5.2 Consent

#### *In person*

Study research staff will obtain informed consent prior to the participant undergoing any study activities. This process will involve:

- discussion between the potential participant and their parent/guardian and a trained research project staff member about the nature and objectives of the study and possible risks associated with their participation.
- presentation of the approved information leaflet and consent/assent documents. Two different participant information sheets will be used, for younger and older adolescents written in appropriate language.
- the aims will be framed in age and developmentally appropriate language. This will acknowledge that adolescents have different maturities. For younger teenagers (12-14 years), the process will be undertaken with their parents or guardians.
- an opportunity for potential participants and/or their parent/guardian to ask questions.
- contact point where the participant /parent or guardian may obtain further information about the trial from the research team.
- Participants aged 15 years and above will be asked to sign an informed consent form; for participants less than 15 years of age, parents will be asked to sign an informed consent form and teenagers will be asked to sign an assent form.

#### *Via website*

Parents and potential participants will be directed to the trial home page where they will be taken through informed consent/assent process. Informed consent/assent will be obtained prior to the participant undergoing any study activities. This process will involve:

- presentation of the approved information on the web pages (also available in printable leaflet form)
- information will cover the nature and objectives of the study and possible risks associated with their participation;
- participants and/or their parents will be informed that they are able to withdraw from the trial at anytime without giving reasons and without prejudicing his/her further treatment, explanation will be given about the right to withdraw permission to use previously collected data;
- an opportunity for potential participants and/or their parent/guardian to ask questions before signing consent/assent by sending a message to the trial team;
- contact point where the participant /parent or guardian may obtain further information about the trial from the research team.

For younger participants (12-14 years), when the parent consents, an invitation will be sent via email to the adolescent participant. This will take them through a similar but age appropriate assent process. Older participants (15-17 years) will be able to give their own consent to participate and will be given immediate access to the study.

### 5.5.3 Screening

Questions on the trial web site will assess their eligibility for the trial (age 12-17 years, physician diagnosed asthma, under the care of a general practitioner, community or hospital practitioner for their asthma, no co-existent respiratory conditions and not used breathing techniques).

#### **5.5.4 The randomisation scheme**

Participants will be randomised via the study website to the next treatment allocation in the randomisation sequence by the trial team. The list will be generated using block randomisation with variable block sizes with a 1:1 allocation ratio between the intervention and usual management. Those randomised to the intervention will have immediate access to the intervention pages. The control group will be able to access the full intervention website at the end of the trial. The website will alert the study team to a new randomisation by email.

#### **5.5.5 Blinding**

This is an open trial. It will not be possible to blind the breathing retraining intervention. Control participants will also gain access to the full intervention website once they have finished participating in the trial.

#### **5.5.6 Baseline data**

Minimal baseline information will then be collected:

- Basic demographic information: age in year, gender;
- Asthma history including treatment and any hospitalization;
- Any other significant health issues.

These data will be collected using an online questionnaire that the research team has used in previous studies [28] (Appendix 4).

#### **5.5.7 Trial assessments**

There are three assessments which will be completed online:

- Asthma quality of life: this will be assessed using the validated PedsQL Asthma Module [24].
- Asthma control: this will be assessed with the validated asthma control test [27].
- Healthcare utilisation: this will be assessed using a very short questionnaire.

The Paediatric Asthma Quality of Life Questionnaire will also be completed. As the copy write forbids this to be completed electronically, this will be completed in person or sent by post. The correlation between PedsQL Asthma Module (with and without the additional emotion questions [25] and the Paediatric Asthma Quality of Life Questionnaire will be assessed to ensure that the PedsQL Asthma Module (with and without the additional emotion questions) provides a valid assessment of quality of life.

#### **5.5.8 Long term follow-up assessments**

Participants will be re-assessed after 2 and 6 months. They will be contacted by email with a link to the study website. Instructions on the website will take them through:

- PedsQL Asthma Module
- Asthma control test
- Asthma healthcare utilisation questionnaire

These are the questionnaires they completed at baseline. Additionally, participants in the intervention arm will be asked whether or not they have used the breathing exercises.

Participants will receive two email/text reminders.

Additionally, they will complete the paediatric asthma quality of life questionnaire on paper after 2 and 6 months. This will either be at a face to face visit, will be posted to the study team, returned via email or completed over the telephone.

### **5.5.9 Qualitative interviews**

The qualitative study will collect data both during participation and after participants finish using BREATHE4T. Qualitative interviews will seek to provide an in-depth understanding of the perspective of patients, to inform intervention and trial acceptability and to generate hypotheses about intervention mechanisms of action that can be tested in a larger trial.

Participants and sampling: Patients will be asked whether they would consent to take part in an interview at a later point in the study. Purposive sampling will then be used to select patients from the intervention group to allow for a wide range of views and experiences of the BREATHE4T programme e.g. covering age ranges, gender, asthma severity. We will also interview a small sample of control group participants to understand their experiences of trial participation. Additionally, we intend to interview participants who withdraw / drop out of the intervention arm, in order to understand reasons for doing so, to inform the larger trial design. It is anticipated that 10-20 intervention group patients will be interviewed both during and following the study. Sampling will continue until saturation is reached.

Data collection: Factors that may facilitate or diminish the acceptability of the BREATHE4T programme, adherence to implementation and mechanisms of action of the intervention will be explored, as well as acceptability of trial participation across patient interviews. Interviews will be conducted during months 4, 5 and 6 of the study. Open-ended questions within a semi-structured interview guide will be used to elicit user perspectives and experiences of the intervention, allowing participants to freely describe their experiences and views in their own way and to focus on whatever is most salient to them.

Interviews will be face to face, by telephone or video call and will be audio-recorded and fully transcribed.

Transcriptions will be anonymised (identifiable data removed) using participant numbers. To ensure that we remain open to and grounded in users' perspectives we will carry out inductive thematic analysis of all textual data, triangulated where appropriate with quantitative self-report measures and web usage data. A 10% sample of interviews will be double-coded using the initial thematic framework, to enhance the rigour of the analysis process.

The findings will be used to inform any modifications needed to BREATHE4T programme or the trial procedures for a potential future full RCT.

### **5.5.10 Withdrawal criteria**

Where a participant or their parent or doctor wishes them to withdraw from the intervention, this will happen. Where possible follow up of the participant in the trial will continue. There will be no replacement of withdrawn participants.

### **5.5.11 Trial intervention**

Breathe4T is a digital, self-management intervention for adolescents to control their asthma using breathing retraining exercises. The mobile-friendly website provides information about asthma and how it affects the lungs, as well as how breathing patterns can be dysfunctional, using developmentally appropriate language. Information is presented using short (30sec-2min), engaging video clips featuring a combination of physiotherapists, researchers and young adolescent role models. Users are given tips and information about their practice, including choosing a suitable time and place and building up gradually. Users can plan their practice, log how their practice went and record their confidence in using the breathing techniques in situations. There are 8 sessions to progress through. Each session includes

a video of a peer role model demonstrating the breathing exercise with a voiceover to explain the technique. Written, step-by-step instructions are also provided, in addition to a short description of the benefits of each exercise. All features and sessions can be accessed via a main dashboard where participants are also able to tailor the intervention to allow parental involvement, reminders around inactivity and their preferred format of notifications (email or text). A “frequently asked questions” section answers the common queries and concerns of breathing retraining. Users can view their asthma progress on a chart, which upon logging in requests information about their inhaler (preventer) use across time. The intervention has been designed to be easy to use on a mobile-device and with engaging colours and images.

### 5.5.12 Trial restrictions

There are no trial restrictions.

## 6 SAFETY

### 6.1 Definitions

| Term                               | Definition   |
|------------------------------------|--|
| Adverse Event (AE)          | Any untoward medical occurrence in a participant including occurrences which are not necessarily caused by or related to the trial intervention.   |
| Serious Adverse Event (SAE) | 
A serious adverse event is any untoward medical occurrence that:
 
 
• results in death
 
• is life-threatening
 
• requires inpatient hospitalisation or prolongation of existing hospitalisation
 
• results in persistent or significant disability/incapacity
 
• consists of a congenital anomaly or birth defect
 
 
Other ‘important medical events’ may also be considered serious if they jeopardise the participant or require an intervention to prevent one of the above consequences.
 
NOTE: The term "life-threatening" in the definition of "serious" refers to an event in which the participant was at risk of death at the time of the event; it does not refer to an event which hypothetically might have caused death if it were more severe.
 |
| non-IMP SUSAR               | 
Non-IMP SUSAR is an SAE that occurs in a non-IMP trial and is:
 
 
a) “Related” – that is, possibly, probably or definitely resulted from administration of any of the research procedures, and
 
b) “Unexpected” – that is, the type of event is not listed in the protocol as an expected occurrence.
 
  |

“Severe” is used to describe intensity of a specific event, which may be of relatively minor medical significance. “Seriousness” is the regulatory definition supplied above.

### 6.2 Operational definitions for (S)AEs

Exceptions including hospitalisation as a SAE are:

- Routine treatment or monitoring of the studied indication not associated with any deterioration in condition.
- Treatment which was elective or pre-planned, for a pre-existing condition not associated with any deterioration in condition.
- Treatment on an emergency, outpatient basis for an event not fulfilling any of the definitions of serious as given above and not resulting in hospital admission.

Given the nature of the study, related SAEs are unlikely to occur.

### **6.3 Recording and reporting of SAEs**

Participants will be asked to provide details of any potential AEs at the 2 and 6 month follow up assessments. An email alert will be sent to the study team.

For any SAEs, an assessment of seriousness, causality and expectedness will be made by the PI or delegate as per local reporting standard operating procedures.

Where SAEs occur, they will be notified to the Sponsor at [[contact]](mailto:[contact]) within 24 hours of the occurrence or knowledge of the occurrence, using the SAE reporting form. .

Where a non-IMP SUSAR has occurred this must be notified to the sponsor at [[contact]](mailto:[contact]) immediately upon the study teams' knowledge of the event, the sponsor will then notify the REC within 15 days using the SAE report form.

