### **6.4 Responsibilities**

#### Principal Investigator (PI):

Checking whether participants report AEs when they are reassessed at 2 and 6 months.

1. Using medical judgement in assigning seriousness and causality.
2. Ensuring that all SAEs are recorded and reported to the sponsor within 24 hours of becoming aware of the event and provide further follow-up information as soon as available. Ensuring that SAEs are chased with Sponsor if a record of receipt is not received within 2 working days of initial reporting.

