## **7.1 Sample size calculation**

Stage 3 represents a pilot trial so the effectiveness of the intervention is not being evaluated, therefore a formal power calculation is not appropriate. The sample size is based on a 95% confidence interval approach. For each of the expected proportions/means in the key objectives below, the precision to which we would be able to estimate the proportion/mean given this sample size is presented (nQuery and nTerim v4.0).

For the specific pilot trial objectives, the following are descriptions of the precision of our estimates with the stated assumptions:

i. *Recruitment rate*: It is estimated that the percentage of those approached who are randomised is around 30% therefore the approached sample size will be approximately 387 resulting in a half width for the confidence interval of 5%. The widest confidence interval for this approximation results when the percentage of randomised to approached is around 70% giving an approached sample size of 166 and a 95% confidence interval half width of 7%.

ii. *Acceptability and uptake of the intervention*: it is estimated that the uptake rate across those randomised to the intervention will be 90%, with 58 available participants for this estimation; this would result in a confidence interval half width of 8%.

iii. *Number of participants assessed at 6-months*: It is estimated that the dropout rate from the trial will be 20% of those randomised. With 116 participants randomised into the trial this would result in a confidence interval half width of 7% for the estimate of the dropout rate. Even when considering the statistical worst-case scenario of 50% the resulting confidence interval for this sample size has a half width of 9%.

iv. *Mean asthma related quality of life at 6 months in the control group*: with an estimated standard deviation of 1.4 from the UBIOPRED cohort (1), if data from 46 participants are available at 6 months and therefore

available for this estimation, this would give a confidence interval half width of 0.4 units approximately 0.3 standard deviations.

v. *Completeness of data for asthma related quality of life and healthcare utilisation data across the study in the two groups:* this is estimated at 95% across those randomised and still in the trial at 6 months, giving 92 participants available for this estimation therefore giving a confidence interval half width of 5%. Additionally, we plan to interview 10-20 participants in each intervention group.

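### Adverse events are actively sought only by self-report at 2 and 6 months, and a reported hospital admission has no stated link to SAE assessment, so SAE detection can be late and incomplete

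*Combined protocol and SAP*

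**What the plan says.** On detection, section 6.3 states: "Participants will be asked to provide details of any potential AEs at the 2 and 6 month follow up assessments". It continues: "An email alert will be sent to the study team". The Principal Investigator's duty in section 6.4 is tied to the same two points: "Checking whether participants report AEs when they are reassessed at 2 and 6 months". The schedule of procedures in Appendix 1 ticks adverse event assessment at the 2- and 6-month columns and nowhere else. It allows months 2 to 3 for the first and months 5 to 8 for the second.

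On reporting, section 6.3 sets the sponsor notification at "within 24 hours of the occurrence or knowledge of the occurrence, using the SAE reporting form". Section 6.4 has SAEs "reported to the sponsor within 24 hours of becoming aware of the event". Section 6.5 applies a 24-hour limit to deaths, counted from the team's awareness.

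On hospital admission, section 6.1 lists as a criterion for seriousness an event that "requires inpatient hospitalisation or prolongation of existing hospitalisation". Section 5.1 separately collects, as a healthcare utilisation outcome at baseline, 2 and 6 months, "hospital admission for an exacerbation of asthma".

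On loss to follow-up, section 7.1 (iii) says: "It is estimated that the dropout rate from the trial will be 20% of those randomised".

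**The concern.** Section 3 names asthma exacerbation, possibly needing hospital care, as the main risk to participants. An emergency admission of that kind is an SAE under section 6.1, and none of the exceptions in section 6.2 removes it. The event most likely to matter for safety is therefore also one the plan asks about directly, in the utilisation questionnaire. Yet the text gives the answer no safety consequence. Section 5.5.8 lists the questionnaires used at follow-up: utilisation is there, but the adverse event question is not. That question appears only in sections 6.3 and 6.4 and in Appendix 1.

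The setting makes this more important. Participants are aged 12 to 17, are followed largely by email link, and can join through Asthma UK, social media or snowballing with online consent (sections 5.5.1 and 5.5.2). The study team need not be the treating team, and the primary care practices are identification centres only. No query to a GP, hospital or parent is described. A 24-hour rule helps only once somebody knows of the event. The Trial Management Group, the Trial Steering Committee and the sponsor would then review an SAE count that lags behind events and may not match the admission outcome in the same dataset.

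**Working it through.** **1. The plan's own figure.** The only stated figure bearing on non-response is the precision of the dropout rate in section 7.1 (iii): 20% of 116, half-width 7%. Check: 1.96 × √(0.20 × 0.80 / 116) = 0.0728, or 7.3%, which agrees. The documents give no figure for detection delay.

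**2. Gap between scheduled adverse event questions.** Inputs are the nominal times and windows in Appendix 1. Each gap is the difference between consecutive questions, counting randomisation as month 0. The longest gap is the longest possible wait from an event to the next question. The mean wait is Σ(gap²/2) divided by the time of the last question, assuming events spread evenly over that time.

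| Case | Questions at month | Longest gap | Mean wait |
|---|---|---|---|
| Both on nominal dates | 2, 6 | 6 − 2 = 4 months | (2 + 8)/6 = 1.7 months |
| Last one at end of window | 2, 8 | 8 − 2 = 6 months | (2 + 18)/8 = 2.5 months |
| 2-month missed, last on time | 6 | 6 − 0 = 6 months | 18/6 = 3.0 months |
| 2-month missed, last at end of window | 8 | 8 − 0 = 8 months | 32/8 = 4.0 months |

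**3. Participants with no final answer.** 116 × 0.20 = 23.2, so about 23. Using the plan's own rounded figure of 92 still in the trial, 116 − 92 = 24. Some of these will have answered at month 2, so this is the number without a final answer, not the number never asked.

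**4. Link between admission answer and SAE assessment.** Side by side:
- Section 5.1: asthma admission is recorded as an outcome at the same 2- and 6-month assessments.
- Section 6.1: inpatient hospitalisation makes an event serious.
- Section 6.3: the alert sentence follows the adverse event question and names no other trigger.
- Section 6.4: the investigator checks whether participants report adverse events. Nobody is assigned to turn an admission answer into an SAE assessment.
- Section 9: the study team monitors trial data. The Trial Management Group reviews whole-trial data and SAEs at least every 2 months. This review can act only on answers already submitted, so it does not shorten the gaps in step 2.

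Non-asthma admissions are not in the utilisation outcome and rest entirely on the adverse event question.

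**5. Start of the 24-hour clock.** Section 6.3 allows the clock to start at the occurrence or at knowledge of it; section 6.4 starts it at awareness. A clock from occurrence cannot be met for an event first learned of at a scheduled question weeks or months later.

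**6. Deaths.** A participant cannot self-report a death. Section 6.5 starts from awareness and names no route by which the team would become aware.

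**The case against.** The strongest case on the other side is that the team has several ways to hear of an event between assessments:
- Participants and parents have a contact point (section 5.5.2), and a trial doctor becomes involved if a participant reports symptoms that worry them (section 10.1).
- Some participants are interviewed in months 4 to 6, including people who drop out of the intervention arm (section 5.5.9).
- The paper questionnaire may be completed face to face or by telephone (section 5.5.8).
- The study team and the Trial Management Group look at trial data, which include the admission answers (section 9).
- Once an SAE is known, sections 6.3 and 6.4 apply whatever its source.

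The trial is also a small, non-drug pilot that the team classes as low risk, with related SAEs thought unlikely.

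Much of this stands. It rules out saying that serious events can be found only at months 2 and 6. The accurate statement is that these are the only points at which they are solicited. The other routes depend on the participant's initiative, reach a subset, or are periodic, and no text ties any of them to SAE reporting.

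A reader might also infer that an admission entered as healthcare use will never become an SAE. The documents do not support that. Section 6.3 does not restrict the alert to the adverse event question, data review could pick the answer up, and website settings or the local procedures cited in 6.3 may already provide the link. What is established is that the protocol states no such link.

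Nor does it follow that all dropouts go unobserved. Section 5.5.10 keeps people who withdraw from the intervention in follow-up if feasible, and others may have answered at month 2.

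**Conclusion.** The point holds as a weakness in detection, and the plan should be changed. As written, the wait to the next scheduled question can be 4 months with perfect timing and 6 to 8 months with a late or missed assessment. About 23 of 116 participants give no final answer if the planned 20% dropout is right. The mean waits of 1.7 to 4.0 months also assume that events are evenly spread. The missing link between the admission answer and SAE assessment, and the missing route to awareness of a death, rest on reading the text and need no assumption.

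Three stronger readings should be avoided:
- The reporting rule counted from awareness is not itself breached; the fault lies before that clock starts.
- A reader might multiply the adult study's severe-event percentages in section 3 by 116 to count missed SAEs. The documents do not support this: section 6.1 separates severe from serious, and section 3 gives no follow-up length for those percentages.
- A reader might infer that an assessment done at month 5 closes adverse event collection before the 6-month intervention period ends. No text sets such a closing date.

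**What to change.** Amend section 6.3, with matching wording in sections 6.4 and 6.5:

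1. Any positive hospital-admission answer in the utilisation questionnaire triggers the same email alert and SAE assessment as the adverse event question. Reconcile the two sources before the database is locked.
2. Add an open form on the trial website, available to participants and parents in both arms, for reporting a hospital stay or other serious problem between assessments. Mention it in the information sheet and in every reminder. A form open to parents also gives a stated route for learning of a death.
3. Send one single-item message about serious events to participants who miss an assessment, and to the parent where a contact is held.
4. Reconcile the occurrence wording in section 6.3 with the awareness wording in section 6.4 as the start of the 24-hour clock.

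If website settings or local procedures already do any of this, stating it in the protocol is enough. The cost is website configuration and a short amendment to the protocol and information sheet, with no new visits. The downside is a few more alerts to triage and possibly a higher SAE count, which should be read as better detection before it is read as more harm.
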